CRUK	Cancer Research United Kingdom
GP	General Practitioner
HADS	Hospital Anxiety and Depression Scale
NIHR	National Institute for Health Research
ORION	Outcome Registry Intervention and Operation Network
PI	Principal Investigator
PM	Practice Manager
SSM	Skin self-monitoring
RCT	Randomised Controlled Trial
RISP	Research Information Sheet for Practices
SMS	Short messaging service

2. Protocol Synopsis

Title	Skin-Self Monitoring for primary care patients at higher risk of melanoma: a phase II RCT
Short Title	MelaTools SSM Trial
Funding	NIHR- Clinician Scientist Award
Chief Investigator	[name]
Research Purpose	To test a novel skin self-monitoring (SSM) intervention in general practice aimed at promoting timely consulting by people at 'above-population' risk of melanoma
Aims	 To evaluate SSM App use compared with standard information on skin change appraisal and help-seeking among patients at 'above-population' risk of melanoma; To optimise the intervention, to establish its acceptability and to collect all the relevant data to inform a subsequent phase III trial.
Study Design	Phase II, multi-site RCT
Study Setting	Patients with an 'above-population' risk of melanoma will be recruited from general practices in CRN Eastern.
Sample size & recruitment	Based on our recent MelaTools Q study, we anticipate that we will need to approach approximately 2,000 people to have 1,600 completed questionnaires; 400 people (25%) will be at higher risk and eligible, and 50% of these will need to attend the trial consultation in order to reach our target of 200 participants.
Inclusion Criteria	 ≥18 years of age ≤ 75 years of age Ability to read and write for informed consent and smartphone use
Exclusion Criteria	 Severe psychiatric or cognitive disorder Physical disorder severe enough to inhibit the use of a smartphone No smartphone
Randomisation	Patients will be randomised 1:1 to either control or intervention group.
Intervention	All participants in both groups will have a standardised consultation about prevention of skin cancer with the research nurse. Those in the intervention group will also be provided with a SSM App and standardised tuition on use.
Duration of individual's participation	Study participation will last no longer than 12 months; patient-reported outcomes will be collected at baseline, 6 months and 12 months post-consultation.

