9.4 Sample Size and Power Calculation

Based on our recent MelaTools Q study with an identical screening step (response rate of 86%), we anticipate that we will need to approach approximately 2,000 people from 10 general practice waiting rooms to have about 1,600 complete the electronic questionnaire (23). About 25%, 400 people, will be identified as 'above-population' risk and be eligible to participate in the trial. Based on previous research we would expect approximately 50% of these to attend their trial consultation and undergo randomisation in order to reach our target of 200 participants.

We will use information on recruitment, retention, and data completeness, in addition to descriptive statistics for the primary and secondary outcomes measures, and preliminary estimates of effect sizes where appropriate, to inform the sample size calculation for a future phase III trial for this intervention where appropriate.

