9.5 Data Analysis

512

513

514515

516

517518

519

520

521

522

523

524

525

526 527

528

529

530

531

532

533

534

535

536

537

538

539

540

541

542

543

544

545

546

547

548

549

550

551552553

554

555

556

557

558559560

561

562563

All randomised patients will be considered eligible for inclusion in the analysis in accordance with the intention-to-treat analysis principle. As this is a phase II trial, fully describing and characterising the extent and nature of the missing data is an important part of the analysis. For the outcome analysis, appropriate methods for dealing with missing endpoint data will be detailed in the statistical analysis plan and be informed by a blinded review of the data. The baseline characteristics of the two arms will be described using summary statistics. Possible consent bias will be assessed by comparing demographic and clinical variables of participants against those who declined participation, and possible differential attrition will be assessed by comparing baseline characteristics of those who withdraw or die against those who remain in the study. These comparisons will be performed using a two sample t-test (or non-parametric equivalent) for continuous variables and chi-square test for categorical variables. The primary analysis will be a comparison between the two groups on the consultation rate for skin changes/pigmented skin lesion using a Poisson regression model. Patient Interval is expected to be right skewed. We will explore the nature and extent of the skewness and will consider it as a continuous variable in the analysis, but may explore other approaches, including transformation, categorisation, or methods for statistical inference based on bootstrap resampling, as appropriate. Comparisons between groups on continuous secondary endpoints will be undertaken using a linear model that includes the baseline value where applicable. Comparisons between groups on binary secondary endpoints will be performed using logistic regression. The analyses performed on the primary and secondary endpoints will be repeated adjusting for additional baseline covariates as part of a sensitivity analysis. Point estimates of the intervention effect will be presented with 95% confidence intervals and two-sided p-values. Unadjusted p-values from secondary analyses will be interpreted in proper context and be clearly labelled.

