2. INTRODUCTION

- 60 This phase II feasibility randomised controlled trial (RCT) tests a novel intervention of the use of a Skin
- 61 Self-Monitoring (SSM) smartphone application ('App'), and self-monitoring monthly reminders, to
- 62 promote timely consulting for skin changes/pigmented skin lesions by people at above-population risk
- 63 of melanoma.

Aims

59

64

65

66 67

68

69

70

71

72

73

74

75

76

77

78

79

- To assess the effect of using a SSM App compared with standard information about detecting skin cancer on the patient interval (time from first noticing skin change to consultation) among patients at above-population risk of melanoma;
- To obtain preliminary estimates of effect across a range of outcome measures to inform selection of the primary outcome for a definitive phase III trial.

Hypotheses

- The MelaTools SSM Trial intervention will increase the number of consultations for pigmented skin lesions in people at above-population risk of melanoma.
- The MelaTools SSM Trial intervention will be acceptable and will reduce the patient interval (including symptom appraisal and help-seeking intervals) in people at above-population risk of melanoma.
- The MelaTools SSM Trial intervention will not cause significant distress or worry in people at above population risk of melanoma.

80 3. METHODS

- 81 Design
- 82 The phase II trial is a multisite individually randomised controlled trial set in 12 general practices across
- 83 Eastern England. Those who meet the eligibility criteria and consent to participate are randomised 1:1
- 84 into either the control or intervention group. Randomisation is being performed using an online system
- provided by the Clinical Trials Unit based at Kings College London.
- 86 Sample size
- 87 The sample size for this Phase II trial is 200. 2000 people will be approached in order to find 400 high risk
- 88 patients, of whom around 200 are expected to consent, as detailed in the trial protocol (Mills et al,
- 89 2017).
- 90 Framework
- 91 This trial is a superiority trial. Comparisons will be presented on this basis. This is a phase II feasibility
- 92 trial and is not powered as a superiority trial for the primary outcome. Estimates will inform the future
- 93 phase III trial.
- 94 Interim analyses and stopping guidance
- 95 No interim analyses are planned.
- 96 Timing of final analysis
- 97 All outcomes will be analysed collectively at the end of the trial.
- 98 Outcomes
- 99 Primary outcomes

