4. STATISTICAL PRINCIPLES

- 128 Confidence intervals and p-values
- 129 All applicable statistical tests will be 2-sided and will be performed using a 5% significance level. No
- corrections for multiple testing will be made. Where appropriate, 95% confidence intervals will be
- 131 reported.

132 Adherence and protocol deviations

- 133 Adherence
- 134 Adherence to the intervention is not monitored. Those who are adherent to the intervention are those
- who are using the skin self-monitoring (SSM) app regularly (once a month or more frequently). People in
- the intervention group receive monthly reminders to use the SSM app. Follow-up questionnaires do not
- include questions on use of the SSM app.
- 138 Protocol deviations
- 139 Protocol deviations will be classified prior to unblinding of treatment. The number (and percentage) of
- patients with major and minor protocol deviations will be summarised by treatment group with details
- of type of deviation provided. The patients that are included in the ITT analysis data set will be used as
- the denominator to calculate the percentages. No formal statistical testing will be undertaken.
- 143 Use of other SSM apps
- We will describe the apps and the intensity of use, overall and by trial arm
- 145 Differential follow-up
- Data quality checks will focus on any practices without any reported consultations in their patients, and
- on any patients with a large number of reported consultations in the year after randomization. It may
- 148 not be possible to check all practices and patients.
- 149 We will describe the number of practice and patients checked, and any resultant changes to the analysis
- dataset. All changes will happen before the treatment allocation is unblended.
- 151 Analysis population
- 152 All analysis will be intention-to-treat, including all randomised patients according to the treatment they
- were randomised to receive.

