 months and 12 months follow-up.

 Those who do not respond to the follow-up questionnaire initially will receive a reminder email, and a phone call reminder.

 Analysis methods

 Analysis of possible consent bias
- 273 Possible consent bias will be assessed by comparing demographics (age, sex) of participants against
- 274 those who declined participation. These comparisons will be performed using a two sample t-test for
- 275 continuous variables and chi-square test for categorical variables.
- 276 Analysis of possible differential attrition
- 277 Possible differential attrition will be assessed by comparing baseline characteristics of those who
- 278 withdraw or die against those who remain in the trial. These comparisons will be performed using a two
- sample t-test for continuous variables and chi-square test for categorical variables.
- 280 Analysis of non-response
- We will compare baseline characteristics of those who do not respond to follow-up questionnaires and
- to patient interval questionnaires with those who do respond. These comparisons will be performed
- using a two sample t-test for continuous variables and chi-square test for categorical variables.
- 284 Analysis of consultation rate
- 285 Data quality checks

287

288

289

290

291292

293

294

- Plot a boxplot of all the consultation rates
- Plot a histogram of all the consultation rates
 - Looking for extreme values, a priori defined as people with 4 or more consultations for suspected skin cancer in a 12 month period. These will be checked for accuracy with the relevant general practice, and either corrected or confirmed accurate and kept in.
- Plot a boxplot of all the consultation rates, by general practice
 - Looking for general practices with oddly high or low consultation rates (although noting that we do expect some general practices to have 0 consultations). The concern will be if there are some practices with high rates across the board, and others with low rates across the board – that may require following up on.
- 296 Analysis planning
- The protocol specifies Poisson regression for this outcome. This is the standard approach for count data.
- 298 It is possible that there is over-dispersion in consultation rates and that other approaches such as
- 299 negative binomial regression would be better. If this is the case, then it will be important to use a more
- appropriate analysis method in the phase III trial. We will report Pearson over-dispersion statistics to

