- inform analysis choice in the phase III trial. For this analysis, we will use Poisson regression.

- 302 Missing data
- There should not be missing data in this outcome as we assume zero consultation rates are true zeros.
- 304 Statistical analysis
- 305 First, we will describe the pre- and post- intervention consultation rates overall and by group,
- 306 summarising using median (IQR) and mean (SD). We will not perform a statistical test, but this will be
- 307 useful information for sample size calculations for the phase III trial.
- The main analysis will be an unadjusted Poisson regression.

Consultation rate, post =
$$\exp(\beta_0 + \beta_1 \times (Intervention))$$

- 309 In Stata code
- 310 glm consult_post i.treat, family(poisson)
- 311 A sensitivity analysis will adjust for demographic information and include a random effect for general
- 312 practice.

Consultation rate, post

=
$$\exp(\beta_0 + \beta_1 \times (Intervention) + \beta_2 \times (Female) + \beta_3 \times (Age in years) + b_1)$$

- Where $b_1 \sim N(0, \sigma_1^2)$ is a random effect to capture GP effects.
- 314 In Stata code
- meglm consult_post i.treat i.female c.age, family(poisson) || practice:
- 316 We will explore the impact of allowing for non-linear associations with age, by introducing a
- 317 changepoint at 65 years.
- 318 Analysis of patient interval among patients who have had a consultation
- 319 Data quality checks

- Plot a boxplot of all the patient intervals
- 321 Plot a histogram of all the patient intervals
- We know from Lyratzopoulos et al (2015) that the quartiles of the patient interval for a different sample of patients with melanoma were Min: 0, Q1: 0, Q2: 21, Q3: 69, pct90:
- 324 234 days. We will have concerns about either data quality or generalisability if more
- 325 than 25% of patients have a patient interval of 80+ days.
- 326 Analysis planning
- 327 The protocol specifies standard linear regression, and includes flexibility on the particular analysis in
- 328 case data are highly skewed.
- 329 We will use linear regression to analyse these data. We will also tabulate consultations by trial arm and
- whether the patient interval was more (or less) than 21 days.

- 331 Missing data
- We expect missing data in this outcome, because it is based on a survey of patients and not all patients
- will respond.
- In the first instance, we will compare rates of missing data between the intervention and control groups.

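### The primary Poisson analysis of consultation counts keeps model-based standard errors, so its interval and p-value are too optimistic if the counts are over-dispersed

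*Protocol*

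**What the plan says.** Protocol section 9.5 defines the primary analysis as a "comparison between the two groups on the consultation rate for skin changes/pigmented skin lesion using a Poisson regression model" and promises 95% confidence intervals and two-sided p-values for intervention effects.

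The SAP takes this up in section 6, Analysis of consultation rate. Under Analysis planning it says: "It is possible that there is over-dispersion in consultation rates and that other approaches such as" negative binomial regression might suit the data better. If so, a more appropriate method is to be used in phase III, and Pearson statistics will be reported to inform that choice. For the present trial: "For this analysis, we will use Poisson regression".

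The Stata line for the main model reads "glm consult_post i.treat, family(poisson", then the closing bracket and nothing more. It has no robust-variance option and no scale option. The sensitivity models are also Poisson. They add sex, age (linear, then with a changepoint at 65 years) and a random effect for general practice.

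Table 3 in SAP Appendix A has places for the Pearson statistic, the rate ratio, its 95% interval and a p-value. SAP section 4 adds: "All applicable statistical tests will be 2-sided and will be performed using a 5% significance level". SAP section 3, Framework, presents the comparison as superiority but says that the trial is not powered for it.

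**The concern.** A Poisson model sets the variance of each count equal to its mean, and the default standard error relies on that. If visits cluster within patients, for example because one lesion leads to several visits, the variance exceeds the mean and the standard error of the log rate ratio is too small. The practice random effect in the sensitivity models absorbs only variation between practices. So no planned analysis of this trial corrects the interval for extra variation between patients.

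What is at stake is the uncertainty statement for a primary outcome. The trial exists to supply preliminary effect estimates and to help choose the phase III primary outcome (protocol sections 6.2 and 9.4). An interval that is too narrow would make the consultation rate look better estimated than it is.

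**Working it through.** **Inputs from the documents.** The test level is 5%, two-sided (SAP section 4). On size, "The sample size for this Phase II trial is 200", and allocation is 1:1 (protocol synopsis), so about 100 per arm. The 200 comes from the recruitment funnel in protocol section 9.4: 1,600 × 0.25 × 0.5 = 200. No power figure is stated.

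**Inputs that are assumed.** The documents give neither a mean consultation rate nor a dispersion. The range used is a mean of 0.1 to 1.0 consultations per patient-year and phi of 1 to 3.

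**Formula.** With true variance phi × mean, the model-based standard error is too small by √phi. Hence

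- actual two-sided error = 2 × [1 − Φ(1.96/√phi)];
- coverage of the nominal 95% interval = 1 − that error;
- correct log-scale interval = planned interval × √phi.

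**Reproducing the nominal level.** At phi = 1, 2 × [1 − Φ(1.96)] = 5.0%, as the SAP states.

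**Results.** The simulated column comes from 20,000 null trials per setting, with 100 per arm, Poisson counts at phi = 1 and negative binomial counts above it, and means 0.1 to 1.0. The test is a Wald test with standard error √(1/S0 + 1/S1), where S0 and S1 are the arm totals.

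| phi | 1.96/√phi | Actual error, formula | Coverage | Interval should be wider by | Actual error, simulated |
|---|---|---|---|---|---|
| 1 | 1.96 | 5.0% | 95% | 0% | 4.4–5.0% |
| 1.25 | 1.75 | 8.0% | 92% | 12% | 6.8–8.0% |
| 1.5 | 1.60 | 11.0% | 89% | 22% | 9.3–10.9% |
| 2 | 1.39 | 16.6% | 83% | 41% | 14.3–16.6% |
| 3 | 1.13 | 25.8% | 74% | 73% | 22.1–25.7% |

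**Example.** Assume a mean of 0.3 in both arms, so 30 consultations per arm and a rate ratio of 1.0. The planned standard error is √(1/30 + 1/30) = 0.258, which gives an interval of 0.60 to 1.66. At phi = 2 the standard error is 0.258 × 1.414 = 0.365, and the interval should be 0.49 to 2.05.

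**Remedies in the same simulation.** Robust errors gave 4.3–6.4% for phi up to 2. At phi = 3 they gave 5.8–8.0%, worst at mean 0.1 (about 10 events per arm). Pearson-scaled errors gave 4.5–5.5% for means 0.2 to 1.0 and 2.8–4.5% at mean 0.1. The simulation used the same phi in both arms, which is the assumption that Pearson scaling makes, so that comparison favours scaling somewhat.

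**The case against.** The best defence is that the choice is deliberate and open. The SAP names the risk, names the alternative, keeps the model that the protocol pre-specified, and prints the Pearson statistic beside the result in Table 3 and again for the main and sensitivity models in Appendix 2 Table 2. Means, standard deviations and histograms of the counts by arm are also planned. A reader can multiply the log-scale half-width by the square root of the Pearson statistic. The trial is an unpowered feasibility study with no multiplicity correction, so strict type I error control is not what the next step rests on.

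Most of this stands, and it lowers the priority of the point. It does not remove it: the printed interval and p-value remain uncorrected, and the stated purpose of the Pearson statistic is the phase III model, not the present interval.

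A reader might infer three stronger things that the documents do not support.

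- **That the interval will in fact be too narrow.** The SAP calls over-dispersion possible, not expected, and no figure sizes it.
- **That many patients with no consultations would show over-dispersion.** They would not: at an assumed mean of 0.3 a pure Poisson model already gives exp(−0.3) = 74% zeros, against 0.5^0.3 = 81% for a negative binomial with phi = 2.
- **That the effect estimate passed to phase III is distorted.** It is not, because over-dispersion leaves the rate ratio unbiased.

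**Conclusion.** The point holds conditionally. The plan recognises a threat to its primary inference and leaves the primary interval and p-value unprotected against it. If phi exceeds 1 they are too optimistic: about 8%, 11% and 17% actual error at phi 1.25, 1.5 and 2, with log-scale intervals that should be 12%, 22% and 41% wider. These figures rest on assumed dispersion and, for the simulation, on assumed means and 100 patients per arm. At phi = 1 the planned analysis is valid.

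This is an advisable and inexpensive improvement, not a defect that undermines the trial.

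**What to change.** **Main model.** Keep the Poisson point estimate and append `vce(robust)` to the Stata line, so that the interval and p-value in Table 3 are robust. If events are very sparse, use Pearson scaling, `scale(x2)`, instead. The SAP should define very sparse in advance, on the pooled count and blind to arm. Continue to report the Pearson statistic.

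**Sensitivity model with the practice random effect.** Change the family to negative binomial. Do not use a sandwich variance there, because its independent units would be the 12 practices named in SAP section 3, too few for it to be reliable.

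**Cost.** One option in the main Stata line, one change of family, and a sentence or two in the SAP. The protocol's Poisson model and the main model's rate ratio are unchanged. The interval widens by about √phi when over-dispersion is present, and almost nothing is lost when it is absent.

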6.2 Aims

- **1.** To assess the effect of using a SSM App compared with standard information on the patient interval among patients at above-population risk of melanoma;
- **2.** To obtain preliminary estimates of effect across a range of outcome measures to inform selection of the primary outcome for a definitive phase III trial.

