8.1 Study Design and Outcomes

We applied the well-established MRC methodological framework for the design and evaluation of complex interventions to provide preliminary data to inform the design of this phase II RCT (24, 25). As this is a feasibility trial there will be two primary outcomes:

Primary Outcome/s

- a. Consultation rates for any skin changes/pigmented skin lesions presented to their GP/practice nurse during the 12 months following the trial consultation compared with the 12 months prior to the trial and;
- b. The patient interval (PI) for all skin changes/pigmented skin lesions presented to their GP/practice nurse during the 12 months following the trial consultation.

Secondary Outcomes will include:

- a. Patient-Reported Outcomes, including: sun protection habits, skin self-examination, melanoma worry and perceived melanoma risk, self-efficacy for consulting without delay; anxiety, depression and quality of life;
- **b.** Trial feasibility and acceptability, including: data on patient recruitment, attrition, and response rates to outcome measures to inform decisions about a future phase III trial;
- c. Melanoma incidence across participating practices, to contextualise trial findings and after 5 years.

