8.8 Measures

8.8.1 Patient Reported Outcome Measures (PROMs)

For all participants, these data will be collected at baseline, 6 months and 12 months post-trial consultation:

- a. Demographics and clinical variables: age, gender, marital status, postcode, highest education level, occupation, past history of skin cancer (melanoma, SCC, BCC), skin and hair type (density of freckles on arms before age 20, natural hair colour at age 15, number of severe sunburns aged 2-18), number of raised moles on both arms, measured at baseline only.
- b. Sun protection habits scale: developed by Glanz et al in the US for a multicomponent skin cancer prevention programme, this comprises 5 items measured using a 4 point Likert scale, and relating to use of sun protection, sun and sunbed habits, and episodes of sunburn in the previous year (27).
- c. Skin Self-Examination benefits and barriers scale: validated by Manne and Lessin in the US among melanoma survivors, and developed from previous work on mammography and family members of patients with colorectal cancer (28). The benefits scale has seven items (α =.71) and the barriers scale has ten items (α =.74).

411 d. Melanoma Worry Scale (MWS): validated by Moye et al in the US (29), an adapted from 412 the Breast Cancer Worry Scale (30), this measure comprises four items, scored 1 to 4, with 413 possible scores ranging from 4 to 17, and higher scores indicating higher levels of worry.

e. Perceived Melanoma Risk: drawn from Manne and Lessin's measures (28), these two items have been widely used for melanoma and other cancer risk assessments to assess estimated percent risk of developing melanoma, and perceived risk compared with a person of the same age (relative risk).

f. Self-Efficacy for consulting without delay: A 10-item self-completed scale summed to score 10-100, was used in a primary care trial for lung symptoms, and showed good internal reliability (Cronbach α =0.85) (21, 31, 32). It has been adapted for this study, and reduced to 8 items.

g. Hospital anxiety and depression scale (HADS): This 14-item self-completed scale has been widely used to measure distress and has been extensively validated and shown to perform well in a wide range of populations (mean Cronbach α = 0.82; sensitivity and specificity 0.80) (33).

h. SF-12 Quality of life scale: a 12-item version of the SF-36 that is widely used and validated to measure functional health and well-being.

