- 390 There are several other secondary outcomes which do not form part of scales.

391 392 393 394	Statistical analysis and missing data Analysis for these items will be entirely descriptive. We will quantify the amount of missing data, and then describe the distribution of these responses at 0,6,12 months follow-up by trial arm (without any statistical testing).
395 396	If we do see apparent differences then this may suggest that one of these is a good outcome variable for use in the Phase III.
397	We will not present p-values for differences on these outcomes.
398 399	Analysis of melanoma incidence This is just for context, and of course is a useful data quality check.
400 401 402	We will request from PHE ODR the full count of incident cases across these practices in 2013 to 2015 and nationally, without any demographic information. We will then calculate the rate as the total number of cases divided by the total practice list size / population of England.
403 404	This avoids any identifiability concerns around patients registered at these practices who have not consented to take part in the trial.

405	Harms
406	No specific adverse event information has been collected for this trial, beyond outcome measures
407	already described.
408	Statistical software
409	All analysis will be carried out in Stata v15.
410	Additional analyses
411	We have described several exploratory analyses looking for evidence of differential impact to help in
412	design of the analysis for the phase III trial.
413	

REFERENCES

414

423

424

425

426

427

428

429

430

431

432

433

434

435

[figure not shown]
436

437

445

- 420 Manne S and Lessin S (2006) Prevalence and correlates of sun protection and skin self-examination 421 practices among cutaneous malignant melanoma survivors. *J Behav Med* **29**: 419-34, 422 doi:10.1007/s10865-006-9064-5

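### The protocol promises lifetime melanoma risk a baseline-adjusted effect estimate with a confidence interval; the SAP only tabulates it by arm

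*Protocol*

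**What the plan says.** Protocol 8.1 lists among the patient-reported secondary outcomes "sun protection habits, skin self-examination, melanoma worry and perceived melanoma risk, self-efficacy for consulting without delay", and SAP section 3 repeats the list. Protocol 8.8.1 describes perceived risk as two items, "estimated percent risk of developing melanoma, and perceived risk compared with a person of the same age", within the set collected at baseline, 6 and 12 months. The SAP (section 6 and Appendix B) records the first on a 0-100% range and the second in five ordered categories scored 1 to 5.

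On analysis, protocol 9.5 says: "Comparisons between groups on continuous secondary endpoints will be undertaken using a linear model that includes the baseline value where applicable". It adds: "Point estimates of the intervention effect will be presented with 95% confidence intervals and two-sided p-values". Protocol 6.2 gives the second aim as "To obtain preliminary estimates of effect across a range of outcome measures", to help choose the phase III primary outcome.

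For outcomes outside the nine scales, which include both perceived-risk items, the SAP says: "Analysis for these items will be entirely descriptive". It rules out tests and p-values, but says that differences seen in the tabulations may point to a good phase III outcome. Table 5 gives lifetime risk as mean (SD) by arm at 6 and 12 months.

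**The concern.** The two texts give different analyses for the same named endpoint. The protocol leaves missing-data methods to the SAP, but it does not leave open whether a continuous secondary endpoint gets an effect estimate.

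The second aim is at stake. Perceived risk remains a possible phase III outcome under the SAP, but it would be judged by looking at separate arm summaries. The nine scales would be judged on a baseline-adjusted difference with an interval. A reader who subtracts the Table 5 means gets a contrast that takes no account of chance baseline imbalance and is less precise than the data allow.

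**Working it through.** **Comparing the texts for the percent lifetime-risk item**

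1. Is it a secondary endpoint? Yes. Perceived melanoma risk is named in protocol 8.1 and SAP section 3, and protocol 8.8.1 makes the percent item part of it.
2. Is it continuous, with a baseline value? Yes. It runs from 0 to 100%, and SAP Table 1 reports its baseline mean (SD).
3. What does protocol 9.5 require? A linear model with the baseline value, a point estimate, a 95% confidence interval and a p-value.
4. What does the SAP provide? Arm-level mean (SD) in Table 5. That table has no column for a difference or interval, and Table 4, which has both, covers only the nine scales.
5. Is the change explained? No. For consultation rate and for patient interval the SAP states what the protocol specified before giving its own choice, and it dates the exclusion of the sunbed item. It has no such note here. The Appendix B instruction to analyse items individually is not an explanation either: self-efficacy carries the same instruction and is still modelled as a scale.

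**Relative-risk item.** It has five ordered levels. The protocol's linear model applies only if the 1-5 score is treated as numeric. Otherwise only the general sentence on estimates and intervals reaches it.

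**What adjustment would add**

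The plan gives no precision or power figure for this endpoint. Its only relevant number is the target, which reproduces from the stated funnel: 1,600 × 0.25 = 400, and 400 × 0.50 = 200. With 1:1 allocation that is 100 per arm.

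The SD and the baseline to follow-up correlation r are not in the documents. I assume SD 15 to 25 points and r from 0.3 to 0.7. For one follow-up visit with complete data:

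95% CI half-width = 1.96 × SD × √(1 − r²) × √(2/n per arm)

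Example, SD 20, r = 0.5, n = 100: 1.96 × 20 × √0.75 × √0.02 = 4.80 points, against 1.96 × 20 × √0.02 = 5.54 unadjusted.

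| SD (points), 100 per arm | Unadjusted | r = 0.3 | r = 0.5 | r = 0.7 |
|---|---|---|---|---|
| 15 | 4.16 | 3.97 | 3.60 | 2.97 |
| 20 | 5.54 | 5.29 | 4.80 | 3.96 |
| 25 | 6.93 | 6.61 | 6.00 | 4.95 |

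The relative narrowing is 1 − √(1 − r²), whatever the SD or n: 4.6% at r = 0.3, 13.4% at r = 0.5 and 28.6% at r = 0.7. With an assumed 80 per arm responding and SD 20, the half-widths are 6.20 unadjusted and 5.91, 5.37 and 4.43 adjusted. The nine-scale model pools two visits, so its actual precision will differ from these single-visit figures.

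**The case against.** The strongest reply is that this is a feasibility trial, stated not to be powered, with no multiplicity correction. Keeping single items descriptive is open, pre-specified restraint. Protocol 9.4 also asks for effect sizes only where appropriate. This supports leaving out p-values. It does not explain leaving out an estimate and interval that 9.5 promises, because the SAP never says why they would be inappropriate for this item.

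Four stronger readings are tempting, and the documents do not support them:

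- *Sunburn was promised the same analysis.* It is not in the protocol 8.1 list. Protocol 8.8.1 mentions it only as content of the sun protection measure, described as "relating to use of sun protection, sun and sunbed habits, and episodes of sunburn in the previous year". The SAP item has four ordered categories, so it fits neither the linear nor the logistic model in 9.5.
- *The second aim goes unserved.* The aim refers to a range of measures. Both primary outcomes (Table 3) and all nine scales (Table 4) get estimates with 95% intervals. The gap is confined to these items.
- *The baseline values are wasted.* They are tabulated by arm and used in the non-response comparison. They are only not used for adjustment.
- *No effect size can be obtained.* A crude difference and an approximate interval for lifetime risk can be worked out from the means and SDs in Table 5, given the numbers responding. What is lost is the pre-specified, baseline-adjusted presentation.

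It is also fair to say that the precision gain rests entirely on assumed correlations and is small at the lower end.

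**Conclusion.** The point holds for the percent lifetime-risk item: the protocol commits to a baseline-adjusted estimate with a 95% interval, and the SAP withdraws it without saying so. It holds more weakly for the relative-risk item, which the linear-model commitment covers only if the 1-5 score is treated as numeric. It does not extend to sunburn or the other single items.

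The consequence is modest. No primary outcome or scale is affected. The gain in interval width is about 5%, 13% or 29% under assumed correlations of 0.3, 0.5 or 0.7. The mismatch between the documents, and the missing estimate and interval, do not depend on those assumptions. The change is worth making because the data and the model already exist and the SAP keeps these items as possible phase III outcomes.

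**What to change.** In the SAP section on other secondary outcomes, fit the baseline-adjusted multilevel model already specified for the nine scales to lifetime risk. Use the 6- and 12-month values as the outcome and the baseline value as a covariate only. Optionally do the same for the relative-risk score, stating that the 1-5 score is treated as numeric. Add the between-arm difference with its 95% confidence interval to Table 4.

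P-values may stay omitted, with one sentence noting that this departs from protocol 9.5. Sunburn and the remaining single items may stay descriptive. If the sponsor prefers to leave lifetime risk descriptive as well, the SAP should name the departure from 9.5 and give the reason.

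No new data are needed. The cost is a short SAP change, one or two table rows, and one or two more estimates to interpret cautiously in an unpowered trial.
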